**Strabismus:**

Strabismus patients receiving higher doses of BOTOX reported vertical deviation. About 17% of 2058 adults that received a total of 3650 injections for treatment of horizontal strabismus reported vertical deviation. Ptosis was reported in 1%, 16%, and 38% after injections in inferior rectus, horizontal rectus, and superior rectus, respectively. Retro bulbar hemorrhage was reported in 0.3% cases.

In general, local muscle weakness appears to be the most commonly reported and expected event following BOTOX injection in muscles. However, weakness of adjacent muscle tissues, and rarely remote tissues occurring as a result of “spread of toxin effect” have been reported in adult and pediatric patients as well. Events typically observed after any injection procedure including localized pain, inflammation, tenderness, bruising, erythema, and needle-related pain or anxiety have been reported in some clinical trials.

We will recruit obese subjects with pre-diabetes or T2D for the proposed clinical study for 5 visits. After informed written consent is obtained, subjects will be admitted to the Clinical Research Center (CRC), and will undergo upper endoscopic injection of Botox into the duodenal wall. We anticipate that injections of Botox into the duodenal wall will result in significant weight loss and improvements in glucose tolerance and duodenal nutrient sensitivity. Subjects will be studied over a period of 6 months. Subjects will be asked to complete 5 study visits: On the first visit, each subject will undergo an oral glucose tolerance test (OGTT). At visit 2, subjects will undergo an esophagogastroduodenoscopy (EGD) procedure for the delivery of BtX-A to the duodenal wall. Visits 3-5 will be made 1, 3, and 6 months after EGD (Figure 1). On every study visit, body weight and body composition will be recorded and oral glucose tolerance test (OGTT) be performed. Nutrient sensing test will be performed at visits 1 and 3.

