**Post EGD Care:**

- Following completion of EGD procedure and emergence from anesthesia, subjects will be monitored in the VGIES-dedicated post-anesthesia care unit (PACU) prior to discharge.
- Subjects will be provided written instructions regarding potential signs and symptoms of adverse events, including fever, pain, bleeding, and muscle weakness. They will be provided the 24/7 physician call number for any questions or issues that may arise.

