## **9. Reporting of Adverse Events or Unanticipated Problems involving Risk to Participants or Others**

Should a study-related adverse event (AE) result in harm or injury, neither the subject nor their insurance company will be responsible for the cost of immediate medical care provided at Vanderbilt to treat the injury. There are no plans for Vanderbilt to pay for the costs of any additional care.

***Adverse Event Reporting:*** All AEs will be graded according to the following scale:

- 0 = No adverse events or within normal limits
- 1 = Mild; did not require treatment
- 2 = Moderate; resolved without treatment
- 3 = Severe; required professional medical attention
- 4 = Life-threatening or disabling
- 5 = Death

All unanticipated, serious AEs related to the experimental procedures that are Grade 1 or above will be reported immediately to the DSMO (see below) and within 1 day to the IRB. The PIs will review AEs and notify the IRB and NIDDK of any changes needed to the protocol. The annual summary of all adverse events and any audit reports will be sent to the NIH and IRB at the time of continuing review.

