### **(d) Data Safety Monitoring Plan (DSMP).**

- Our DSMP will focus on performance, safety, and care of participants. [name], Columbia University, and [name], Washington University St. Louis, will serve as the Data Safety Monitoring Board (DMSB) for this study.
- This is a pilot study. The DSMB will meet with the PIs at least 3 times. We are planning to initially enroll 3 patients and have the DSMB look at the efficacy and safety data. This will involve an initial meeting to ratify the DSMB, a meeting after the first patient undergoes EGD, and after 3 patients complete enrollment. The next meetings will be at the end of the first and second years, respectively. Progress reports will indicate patient recruitment status, adverse event occurrence, and summary of data collected. The DMSB will assess safety data including development of local or peripheral muscular weakness, bleeding, inflammation, hospitalizations, and other serious adverse events. Based on safety reports, the DMSB will advise and consent modification or termination of the study protocol or the study if it deems such actions to be warranted. Each meeting will be virtual, via zoom. We will send minutes to DSMB members for review and approval after each meeting.
- Participating subjects will be monitored by the physician and nursing staff of the VGIES PACU after recovering from anesthesia for EGD procedure and evaluated by physician prior to discharge.
- The research coordinator will be required to be present to record any AEs and report to the PI or co-investigators promptly of such events.

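### A serious adverse event judged anticipated, such as a bleed or muscle weakness, has no required expedited route to the DSMB that is asked to assess it

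*Combined protocol and SAP*

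**What the plan says.** Section 9 of the combined protocol and SAP gives the rule for immediate reporting: "All unanticipated, serious AEs related to the experimental procedures that are Grade 1 or above will be reported immediately to the DSMO (see below". The same sentence gives the IRB 1 day. The grading scale just above it starts at "0 = No adverse events or within normal limits", then "1 = Mild; did not require treatment", "2 = Moderate; resolved without treatment" and "3 = Severe; required professional medical attention"; Grades 4 and 5 are life-threatening or disabling events and death.

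The Data Safety Monitoring Plan, Section 9(d), sets the board's remit: "The DMSB will assess safety data including development of local or peripheral muscular weakness, bleeding, inflammation, hospitalizations, and other serious adverse events". It lets the board change or end the study on the strength of safety reports. Meetings are listed at the start, after the first EGD, after 3 patients, and at the ends of years 1 and 2, with a stated minimum of three. Progress reports include adverse events, but their timing is not given.

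The same harms are named in advance elsewhere. The closing paragraph of Section 3.2, after the strabismus data, says "local muscle weakness appears to be the most commonly reported and expected event following BOTOX injection in muscles" and mentions rare weakness in remote tissue. Section 7 repeats both points as drug risks and names bleeding as a small EGD risk. The written instructions to subjects (Section 6, Post EGD Care, repeated in Section 7) cover "potential signs and symptoms of adverse events, including fever, pain, bleeding, and muscle weakness".

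**The concern.** An expedited rule exists so that the board hears of a serious harm while it can still affect the next subjects. Here the rule depends on the event being unanticipated. The harms that the protocol foresees are also those that the board is told to watch, so they are the ones most likely to be judged anticipated and to miss the fast route.

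The stake is oversight between meetings. The protocol describes this use of Botox as unexplored, and after the 3-patient meeting the scheduled reviews are far apart. The board's power to modify or terminate the study depends on reports reaching it. Sample size, power and type I error are not affected.

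**Working it through.** The plan states no figure to reproduce. The check is a reading of the rule against the rest of the document, with one subtraction.

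1. **Form of the trigger (Section 9).** Expedite if the event is unanticipated AND serious AND related to the experimental procedures AND Grade 1 or above. Failing any one condition removes the obligation.

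2. **The grade condition.** Grade 0 means no adverse event, so every adverse event has a grade from 1 to 5. Serious AND Grade 1 or above is then the same set as serious alone. The floor filters out nothing. It also sits oddly beside the word serious, since Grades 1 and 2 are events without treatment, and the protocol does not define serious.

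3. **The unanticipated condition.** Apply the rule to related events:

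| Event | Serious | Unanticipated | Expedited |
|---|---|---|---|
| Serious event of a kind named nowhere in the protocol | yes | yes | yes |
| Serious bleed or weakness, judged worse than what was foreseen | yes | yes | yes |
| Serious bleed or weakness, judged foreseen | yes | no | **no** |
| Mild local weakness | no | no | no |

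   Rows 2 and 3 can be the same event. Which row applies rests on a word that the protocol leaves undefined. In row 3 the result is the same at Grade 4 or 5.

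4. **Where a row 3 event goes instead.** The coordinator reports it promptly to the PI or co-investigators (Section 9(d)). The PIs review adverse events and tell the IRB and NIDDK of any protocol changes needed (Section 9). The IRB and NIH receive an annual summary (Section 9). The DSMB sees it in a progress report or at a meeting. None of these is a required expedited report to the DSMB.

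5. **Size of the exposed group.** Inputs: 20 subjects planned (Section 11) and a DSMB meeting after 3 patients (Section 9(d)). 20 - 3 = 17 subjects remain, with scheduled meetings only at the ends of years 1 and 2. The accrual rate is not given, so the number treated between any two consecutive later meetings could be anything from 0 to 17.

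**The case against.** The best defence is that the rule is loosely worded rather than closed. Several stronger readings are tempting, and the documents do not support them.

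- **That bleeding and weakness are excluded outright.** No section labels bleeding as expected; Section 7 calls its chance minimal. The word expected is applied only to local weakness, and Section 7 describes it as temporary. An investigator could reasonably call a serious bleed or serious remote weakness unanticipated and expedite it. This stands: the gap concerns events judged anticipated, and expedited reporting only. The DSMB still sees the events later.
- **That the Grade 1 floor contradicts the word serious.** Severity and seriousness are different attributes, and joined by AND the floor is redundant, not contradictory.
- **That drug effects fall outside the rule.** Section 6 places the Botox injection within the EGD procedure, so the natural reading covers both. Section 7 does separate procedure risk from drug risk, so a clarifying phrase is worthwhile, but no exclusion is shown.
- **That the report has no recipient.** DSMO is a labelling slip. The pointer leads to Section 9(d), which describes one oversight body.
- **That 17 subjects would be treated before the board learned of a serious event.** This is an upper bound. The year-1 meeting may split the group, the meeting count is a minimum, and progress reports may come sooner. There are also calls to subjects at 1 and 7 days and a DSMB meeting after the first EGD.

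These safeguards are real, but they end with the study team or rest on discretion or unstated timing. None obliges anyone to tell the DSMB promptly of a serious event judged anticipated.

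**Conclusion.** The point holds in this limited form. Section 9 ties expedited reporting to events being unanticipated, serious and related, and defines neither of the first two terms. Weakness and bleeding are foreseen in Sections 3.2, 6 and 7, so a serious case judged anticipated has no required fast route to the DSMB, although Section 9(d) asks the DSMB to assess it. The group exposed after the 3-patient meeting is at most 17 of 20 subjects. That bound assumes that all remaining subjects are treated after that meeting with no extra meeting or earlier progress report; the documents do not allow a closer figure. The grade floor is redundant, and the recipient's name needs an editorial correction. The rule should be changed because a short rewording closes the gap; nothing here shows that the DSMB would be kept from seeing these events altogether.

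**What to change.** In Section 9:

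- require every serious AE, regardless of expectedness, to be reported immediately to the DSMB;
- keep the 1-day IRB report for unanticipated, serious, related events;
- define serious and unanticipated, since these two routes rest on them;
- state that the experimental procedures include both the Botox and the EGD;
- delete the Grade 1 floor;
- change DSMO to DSMB, and correct DMSB in Section 9(d).

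A further trigger based on a higher severity grade is not needed to close the gap. The change is one of wording. Its downside is a few more reports to the DSMB in a 20-subject study; the design, sample size and analysis stay as they are.

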### **(d) Data Safety Monitoring Plan (DSMP).**

- Our DSMP will focus on performance, safety, and care of participants. [name], Columbia University, and [name], Washington University St. Louis, will serve as the Data Safety Monitoring Board (DMSB) for this study.
- This is a pilot study. The DSMB will meet with the PIs at least 3 times. We are planning to initially enroll 3 patients and have the DSMB look at the efficacy and safety data. This will involve an initial meeting to ratify the DSMB, a meeting after the first patient undergoes EGD, and after 3 patients complete enrollment. The next meetings will be at the end of the first and second years, respectively. Progress reports will indicate patient recruitment status, adverse event occurrence, and summary of data collected. The DMSB will assess safety data including development of local or peripheral muscular weakness, bleeding, inflammation, hospitalizations, and other serious adverse events. Based on safety reports, the DMSB will advise and consent modification or termination of the study protocol or the study if it deems such actions to be warranted. Each meeting will be virtual, via zoom. We will send minutes to DSMB members for review and approval after each meeting.
- Participating subjects will be monitored by the physician and nursing staff of the VGIES PACU after recovering from anesthesia for EGD procedure and evaluated by physician prior to discharge.
- The research coordinator will be required to be present to record any AEs and report to the PI or co-investigators promptly of such events.

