## 11. Statistical Analyses

Sample Size: We hypothesize that Botox will reduce body weight, improve glucose tolerance, and augment lipid sensing during fasting and post-prandially, in Class I-III obese subjects. Our outcome measures for the effects of Botox are: body weight; area under the curve (AUC) for plasma levels of ghrelin, CCK, GIP, and GLP-1; and glucose AUC. Power calculation based on previous studies was performed using nQuery Advisor software. The number of subjects needed to detect a 15% decrease in body weight ( $n=16$ ), 10-15% decrease in plasma levels of gut peptides ( $n=14-16$ ), and a 10% decrease in glucose AUC ( $n=16$ ) was determined for an estimated 90% power (two-sided type I error rate = 0.05), with effect size of 0.25. We anticipate studying 20 subjects to account for attrition.

Statistical Analysis Plan: We will analyze pre- and post-intervention measurements at 1, 3, and 6 months using one-way repeated measures ANOVA for each outcome. Correlation between visits will be determined by the first-order autoregressive (AR1) rule which assumes that correlation among repeated measures decline exponentially with time. We will also determine the most optimal (1, 3, or 6 months) and inter time point differences for each outcome.

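### After the third-patient look, DSMB meetings follow the clock and not the number injected, and serious events that the protocol anticipates have no stated prompt route to the board

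*Combined protocol and SAP*

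**What the plan says.** Section 9(d) sets up a two-member DSMB and a staged start: "We are planning to initially enroll 3 patients and have the DSMB look at the efficacy and safety data". The early meetings are one to ratify the board, then "a meeting after the first patient undergoes EGD, and after 3 patients complete enrollment". After that: "The next meetings will be at the end of the first and second years, respectively". A minimum of three meetings is stated, and five are listed. On the basis of safety reports the board may advise changing or ending the study. Its remit names muscular weakness (local or peripheral), bleeding, inflammation, hospitalizations and other serious adverse events.

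Section 9 gives the expedited route. Adverse events that are unanticipated, serious and related to the experimental procedures "will be reported immediately to the DSMO (see below) and within 1 day to the IRB". What follows below is the DSMB. No DSMO is named or given powers anywhere.

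Section 11 gives the total: "We anticipate studying 20 subjects to account for attrition". The documents state no accrual period or pace, no interval between injections, and no date from which the first and second years run.

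**The concern.** Section 1 says that this use of the drug has not been explored before. Each subject has a single injection session, which cannot be taken back once given, so safety oversight protects only those not yet injected. A review held after the last injection protects nobody from exposure.

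The plan accepts that review should follow exposure when it stops to look at 3 patients, but it drops that principle for the other 17. From then on the scheduled meetings depend on elapsed time. What happens between them depends on the expedited route, which has two weaknesses: its recipient is undefined, and it leaves out serious events that the protocol already expects. Those include bleeding and muscle weakness, which the board is specifically asked to assess.

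**Working it through.** **Inputs.** Total 20 subjects (sections 5 and 11). First cohort 3, then meetings at the ends of years 1 and 2 (section 9(d)). The accrual pace is not stated, so even accrual over T months is assumed, with the year counted from the start of accrual. Event risks are also not stated; 5%, 10% and 20% are illustrations only.

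**1. The plan's own total.** Section 11 cites "estimated 90% power (two-sided type I error rate = 0.05), with effect size of 0.25". Read 0.25 as the variance of the means divided by SD²(1 − ρ), for one group at four time points. Then λ = n × 4 × 0.25, with 3 and 3(n − 1) degrees of freedom. The smallest n reaching 90% is 16 (power 0.910). The step from 16 to 20 implies 20% attrition: 16/0.80 = 20. The 20 is reproduced on that reading and is the denominator below.

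**2. Injections between scheduled reviews.** After the third-patient meeting, 20 − 3 = 17 remain (85%). The number injected by month 12 is the smaller of 20 and 20 × 12/T, rounded down.

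| Accrual period T | Injected by month 12 | Between third patient and year-1 meeting | Between year-1 and year-2 meetings |
|---|---|---|---|
| 12 months or less | 20 | 17 | 0 |
| 15 months | 16 | 13 | 4 |
| 18 months | 13 | 10 | 7 |
| 24 months | 10 | 7 | 10 |

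So 17 is the worst case. At 18 or 24 months the longest run without a scheduled review is 10. These figures take the third-patient meeting to follow three injections. If completing enrollment means only consent, just the first patient's injection is certain to have been reviewed, and the bound becomes 20 − 1 = 19.

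**3. What the third-patient look can show.** With no events in n subjects, the one-sided 95% upper limit is 1 − 0.05^(1/n). For n = 3 it is 0.632, for n = 8 it is 0.312, and for n = 14 it is 0.193. A clean first look is compatible with a true risk of up to 63%.

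**4. Illustration.** The chance of two or more serious events in a run of m subjects is 1 − (1 − p)^m − m·p·(1 − p)^(m−1).

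| Assumed risk p | m = 17 | m = 10 | m = 7 |
|---|---|---|---|
| 5% | 21% | 9% | 4% |
| 10% | 52% | 26% | 15% |
| 20% | 88% | 62% | 42% |

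These are chances that the events occur between scheduled meetings. They are not chances that the board fails to hear of them.

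**5. The expedited route against the board's remit.** The discharge instructions in section 6 list bleeding and muscle weakness among the possible adverse events. Section 7 mentions a small chance of bleeding and calls local muscle weakness the most commonly reported event. Both are therefore anticipated. Section 9 expedites only unanticipated events, while section 9(d) asks the board to assess both. Read together, a serious bleed in the fifth subject could fall outside the expedited route even if DSMO means DSMB. The only stated ways it reaches the board would then be the next meeting and its progress report; the annual adverse event summary goes to the NIH and IRB.

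**The case against.** The strongest reply is that DSMO is a typing slip. The text points to what follows, and what follows is the DSMB, whose own abbreviation is misspelled in that section. On that reading, unanticipated, serious, related events reach the board at once, and its power to advise change or termination is not confined to meetings. This is probably right. It does not close the gap: the board is not obliged to convene on receiving a report, and anticipated serious events remain outside the route. A serious bleed might be reported as unanticipated in severity, but the plan leaves that to judgment.

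Other safeguards also count:
- The board meets after the first endoscopy, and the three-meeting minimum allows extra meetings.
- The IRB hears of expedited events within a day.
- There are nurse calls at days 1 and 7, a telephone visit at one week, a 24-hour physician line and prompt reporting by the coordinator to the PI.
- The drug's effect is described as reversible, and safety tables from other injection sites are given.

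These help to detect events and support the safety of a small pilot. None of them requires the board to look again before an annual meeting.

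A reader might infer that up to 17 subjects would be injected with no review by anyone able to stop the trial, that only the DSMB could stop it, or that injections would carry on after a serious event. The documents support none of these. The probable meaning of DSMO puts some events before the board at once, the PIs also review events and notify the IRB and NIDDK of protocol changes needed, and the text is silent on whether injections would continue. Nor does it tie the annual meetings to calendar year-ends.

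**Conclusion.** The point holds as a gap in scheduled and required DSMB review. After the third patient, no scheduled meeting depends on the number injected and no event requires one. The expedited route has an undefined recipient and omits anticipated serious events within the board's remit.

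The size depends on accrual. In the worst case, 17 of 20 injections fall between scheduled reviews, which needs all remaining accrual to precede the year-1 meeting. Under even accrual over 18 or 24 months, about 10 or 7 fall before that meeting and the rest fall before the next. The 63% upper limit after a clean first look needs no accrual assumption; it treats subjects as independent with a common risk. The event chances rest wholly on assumed risks and only illustrate the scale.

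**What to change.** 1. Reconcile section 9 with section 9(d) so that expedited reports go to the DSMB.
2. Send every serious event after injection, anticipated or not, to the DSMB promptly, with an ad hoc review.
3. Keep the annual meetings and add reviews tied to exposure, for example virtual meetings once about 8 and then 14 subjects have been injected and had the day-7 call. The runs between reviews would then be about 8 − 3 = 5, 14 − 8 = 6 and 20 − 14 = 6 at any accrual pace, slightly longer if injections go on while a meeting is arranged. The numbers 8 and 14 are examples that split the remaining 17 roughly evenly.
4. Say whether the third-patient meeting counts injections or consents, and when the first year starts.
5. Let the DSMB decide at its ratification meeting whether, and on what criteria, injections are held.

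The cost is protocol wording, about two extra virtual meetings and possible short delays. The sample size and analysis do not change.
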